4.4 Permissible and Prohibited Medications/Treatments

4.4.1 Permissible Medications/Treatments

Medications which are not specifically prohibited in Section 4.4.2 are allowed, with the following clarifications and restrictions:

The following medications for the acute treatment of migraine are allowed during the study:

- any triptan
- any ergot derivative
- any opioid
- any other form of analgesic (including acetaminophen)
- any NSAID agent
- any antiemetic agent

Aspirin up to 325 mg/day is allowed for cardiac prophylaxis.

SSRIs or SNRIs will be permitted provided that treatment is stable for at least 60 days prior to screening (Visit 1) and continues without change in dose throughout the study.

Therapy considered necessary for the participant's welfare may be given at the discretion of the investigator. If the permissibility of a specific medication/treatment is in question, please contact the sponsor.

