4.4.2 Prohibited Medications/Treatments

The following medications are prohibited 30 days prior to Visit 1 (unless otherwise indicated) and throughout the study period:

- Strong and moderate CYP3A4 inhibitors, including but not limited to: systemic (oral/IV) itraconazole, ketoconazole, fluconazole; erythromycin, clarithromycin, telithromycin³; diltiazem, verapamil; aprepitant, cyclosporine, nefazodone³, cimetidine, quinine, and HIV protease inhibitors (see [Attachment 12.2](#))
- Strong and moderate CYP3A4 inducers, including but not limited to: barbiturates (eg, phenobarbital and primidone), systemic (oral/IV) glucocorticoids, nevirapine, efavirenz, pioglitazone, carbamazepine, phenytoin, rifampin, rifabutin, and St. John's wort (see [Attachment 12.2](#))

Strong OATP1B1 inhibitors (eg, gemfibrozil³, cyclosporine)

- Drugs with narrow therapeutic margins with theoretical potential for CYP drug interactions (eg, warfarin)
- Medications with demonstrated efficacy for the prevention of migraine (eg, amitriptyline, propranolol, topiramate) are prohibited when used for any indication other than migraine prevention. See [Attachment 12.3](#).
 - Participants taking **one** medication with demonstrated efficacy for the prevention of migraine may be randomized provided that in the opinion of the investigator:
 - Dose has been stable and the medication has been well-tolerated for at least 12 weeks prior to Visit 1 AND
 - Participant is willing and able to maintain at a stable dose and dosage regimen during the study, which should be assessed to ensure compliance at each study visit
 - Enrollment of participants with current use of a migraine prevention medication will be capped at ~15%

³not approved in Japan

- Therapeutic or cosmetic botulinum toxin injections (eg, Dysport[®], Botox[®], Xeomin[®], Myobloc[®], Jeuveau[™]) into areas of the head, face, or neck within 6 months prior to Visit 1 and throughout the study period
- Acupuncture, noninvasive neuromodulation devices (eg, transcutaneous supraorbital neurostimulator, single pulse transcranial magnetic stimulator, vagus nerve stimulator), cranial traction, nociceptive trigeminal inhibition, occipital nerve block treatments, or dental splints for headache, within 4 weeks prior to entry into the baseline phase at Week – 4 or at any time during the study (including the Week – 4 to Day 1 baseline phase)

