12.2 Examples of Prohibited Medications

The following medications are prohibited 30 days prior to screening and throughout the study period:

Strong OATP1B1 inhibitors, eg, gemfibrozil (Lopid™)*, cyclosporine

	Strong/moderate CYP3A4 inducers	Strong/moderate CYP3A4 inhibitors
Anti-Depressants/ Anti-Anxiety	Barbiturates 
 • Amobarbital (Amytal™) • Aprobarbital (Alurate™)* • Butalbital (Fiorinal™, Fioricet™)* • Butobarbital (Busodium™, Butisol™)* • Mephobarbital (Mebaral™)* • Pentobarbital (Nembutal™) • Phenobarbital (Luminal™, Solfoton™) • Secobarbital (Seconal™) 	Nefazodone (Serzone™)*
Anti-Seizure	Carbamazepine (Atretol™, Carbatrol™, Epitol™, Equetro™, Tegretol™) Oxcarbazepine (Trileptal™)* Phenytoin (Dilantin™, Phenytek™) Primidone (Myidone™, Mysoline™)	
Diabetes	Pioglitazone (Actos™) Troglitazone (Rezulin™, Resulin™)*	
Antiemetic		Aprepitant (Emend™)
Anti-Hypertension		Diltiazem (Cardizem™) Verapamil (Calan™, Calan SR™)
Glucocorticoid (Systemic)	Betamethasone (Celestone™) Dexamethasone (Baycadron™, DexPak™) Hydrocortisone (Cortef™) Methylprednisolone (Medrol™) Prednisolone (Prelone™) Prednisone (Deltasone™) Triamcinolone (Kenalog™)	
Antibiotics	Rifabutin (Mycobutin™) Rifampicin/Rifampin (Rifadin™, Rifater™, Rimactane™)	Erythromycin (Benzamycin™, EryTab™) Clarithromycin (Biaxin™) Telithromycin (Ketek™)
Anti-Fungal		Fluconazole (Diflucan™, Trican™) Itraconazole (Sporanox™) Ketoconazole (Nizoral™)
Anti-HIV	Efavirenz (Stocrin™, Sustiva™) Nevirapine (Viramune™)	Indinavir (Crixivan™) Nelfinavir (Viracept™) Ritonavir (Norvir™) Saquinavir (Fortovase™, Invirase™)
Immune Suppressant		Cyclosporine - Oral/IV only (Neoral™, Sandimmune™)
Others	St. John's wort Enzalutamide (Xtandi™) Modafinil (Provigil™) Armodafinil (Nuvigil™)*	Buprenorphine (Cizol™, Subutex™, Suboxone™) Quinine

Drugs with narrow therapeutic margins with potential for CYP drug interactions	Warfarin (Coumadin™) Digoxin (Digitek™, Lanoxin™, Digox™) Cisapride (Prepulsid™, Propulsid™)* Pimozide (Orap™)
Non-pharmacologic headache interventions:	Acupuncture Non-invasive neuromodulation devices (eg, transcutaneous supraorbital neurostimulator single pulse transcranial magnetic stimulator vagus nerve stimulator) Cranial traction Nociceptive trigeminal inhibition Occipital nerve block treatments Dental splints for headache

*not approved in Japan

The following treatments are prohibited 6 months prior to screening and throughout the study period:

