12.3.1 List of Migraine Preventive Medications With Proven Efficacy

Below is a list of migraine preventive medications considered effective or probably effective sorted by mechanism of action. Of note, topiramate and valproic acid derivatives are considered separate categories. A history of inadequate response (based on inadequate efficacy or inadequate tolerability) to more than 4 of these medications (2 of which have different mechanisms of action) will exclude the participant from the study.

Pharmacologic Category	Drug Name (all regions unless otherwise noted)
Antiepileptic	Valproic acid, sodium valproate, divalproex sodium Topiramate
Tricyclic antidepressant	Amitriptyline Nortriptyline
Beta-blockers	Metoprolol Bisoprolol Atenolol Nadolol Propranolol Timolol
Calcium channel blocker	Flunarizine Lomerizine (Japan) Verapamil (Japan)
Angiotensin receptor blocker (ARB)	Candesartan
Angiotensin-converting enzyme (ACE) inhibitor	Lisinopril
Serotonin-norepinephrine reuptake inhibitor (SNRI)	Desvenlafaxine Venlafaxine
Miscellaneous	Oxetorone (Europe), pizotifen (Japan, Taiwan, Korea, Australia, and Europe)

Source: [Evers 2009](#), [Hoffmann 2014](#), [Schürks 2008](#), [Silberstein 2012](#), [Steiner 2007](#).

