12.3.2 Criteria for Determining That a Prior Migraine Preventive Medication has Been Failed

The criteria below should be used to determine how to stratify each participant based on the number of prior migraine preventive medications failed with unique mechanisms of action. Failure of a migraine preventive medication can be assessed on the basis of tolerability or efficacy and is based on investigator judgment.

- For efficacy, investigators must consider:
 - Failure is defined as no meaningful reduction in frequency of migraine days after an adequate trial of at least 2 months at generally accepted therapeutic doses, per investigator judgement and participant interview.
 - Medications must have been started within the past 7 years.
 - Note the following for participants who are currently taking a stable dose of one of the migraine prevention medications listed and meet the efficacy criteria:
 - If the participant meets all study entry criteria, this participant is eligible to be randomized provided that the participant agrees to continue to take this migraine preventive medication for the duration of the study.
 - This medication should be considered as one of the failed drugs for the prevention of migraine.
 - Enrollment of participants with current use of a migraine prevention medication will be capped at ~15%.
- For tolerability, investigators should consider:
 - Failure is defined as discontinuation of a drug treatment due to adverse effects.
 - In assessing failure of a migraine preventive drug on the basis of inadequate tolerability, the entire medical history can be considered. For example, a participant who tried and discontinued topiramate 10 years ago for cognitive clouding should be considered to have failed this treatment.

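### Verapamil is prohibited throughout the study, yet for Japan it is also listed among the preventives that a stable user may continue, and the eligibility text does not fully settle which rule governs

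*Protocol*

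**What the plan says.** Protocol 4.4.2 begins with drugs that may not be taken from 30 days before Visit 1 until the study ends. Its first bullet covers strong and moderate CYP3A4 inhibitors, with examples that include "diltiazem, verapamil; aprepitant, cyclosporine". Attachment 12.2 repeats the entry in its inhibitor column as "Verapamil (Calan™, Calan SR™". Neither place makes an exception by region or by reason for use.

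Attachment 12.3.1 lists the preventives regarded as having proven efficacy. Its calcium channel blocker row reads "Flunarizine Lomerizine (Japan) Verapamil (Japan", so verapamil counts as such a preventive in Japan and nowhere else.

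A later bullet of 4.4.2 deals with preventives. It bars them for indications other than migraine prevention, refers to Attachment 12.3, and says that a participant taking one "medication with demonstrated efficacy for the prevention of migraine may be randomized provided that in the opinion of the investigator" two conditions hold: the drug has been stable and tolerated for at least 12 weeks before Visit 1, and the participant will keep it stable during the study. Attachment 12.3.2 says, of a current user of a listed drug who meets all entry criteria, that "this participant is eligible to be randomized provided that the participant agrees to continue to take this migraine preventive medication for the duration". Neither text excepts verapamil.

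**The concern.** For one kind of participant, a person in Japan whose single stable preventive is verapamil, two bullets of the same section point in opposite directions. One prohibits the drug throughout. The other makes its continuation a condition of entry.

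Three things are at stake:

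- **Eligibility.** Two sites in Japan could decide the same case differently, each with a passage in support.
- **Exposure.** If such a participant were enrolled, use of a drug that the protocol bars as a CYP3A4 inhibitor would be continuous for 12 weeks, because the allowance requires it.
- **Classification.** Whether verapamil is continued, or was stopped before screening, determines Current Use or Past Use. Whether its use is a protocol deviation depends on which passage is read.

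**Working it through.** No arithmetic decides this point, so the passages are set against each other.

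1. **Does the prohibition reach Japan?** Protocol 4.4.2 footnotes telithromycin, nefazodone and gemfibrozil as not approved in Japan, and Attachment 12.2 uses asterisks for the same purpose. Verapamil carries neither mark. The prohibition therefore applies in Japan.

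2. **Does the 12.3.1 entry reach current use?** The list has three uses: the exclusion for inadequate response to more than 4 medications, stratification by past use and failures, and, through the pointer in 4.4.2, the allowance for one current preventive. Naming verapamil conflicts with nothing in the first two. No text limits the entry to those two.

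3. **Is there a precedence rule?** The opening sentence of Protocol 4.4.1 makes its permissions yield to 4.4.2. Here the prohibition and the allowance both sit inside 4.4.2, so that sentence cannot decide between them.

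4. **Do the exclusion criteria decide?** Protocol 8.3 requires that no exclusion be met, and 12.3.2 requires that all entry criteria be met. Two exclusions in Protocol 4.3 bear on the case. Exclusion 5 removes a current user who is unwilling or unable to maintain the preventive. Exclusion 6 removes someone who requires a drug on the 4.4.2 or 12.2 list that cannot be discontinued or switched. This gives three cases:
   - The participant is on verapamil and cannot stop or switch. Exclusion 6 applies, so the participant is ineligible.
   - The participant stopped verapamil at least 30 days before Visit 1. The prohibition is respected, the drug is past use, and there is no conflict.
   - The participant is on stable verapamil, could stop or switch, and is willing to continue. Exclusion 5 does not apply, and by its wording neither does exclusion 6. The preventive bullet of 4.4.2 admits the participant, while the CYP3A4 bullet forbids the drug. This case is open.

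5. **Where the answer is used.** Current or past use is a randomization stratum (Protocol 5.4), a factor in the primary model (Protocol 7.3.1; pooled into a single Current Use level in SAP Table 10.1-2), a subgroup (SAP 12.2), and the basis of a separate adverse event table (SAP 11.1). SAP 16.10 derives Current Use from preventives ongoing at screening, using a medication list supplied by the clinical team, and describes no check against the prohibited drugs. That list is not in the documents. If it follows 12.3.1, a verapamil user would be coded as an ordinary Current Use participant. Deviations are classified in a separate specification (SAP 8.0), which is also not in the documents.

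6. **Scale.** The cap on current use is about 15% of about 750 participants: 0.15 × 750 = 112.5, or about 112. That covers every preventive in every region. Current verapamil users in Japan are a subset of unstated size.

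**The case against.** The best answer is that prohibitions accumulate. A drug that appears under two headings must clear both, and the allowance is nested under the preventive bullet, so it most naturally qualifies only that bullet. Exclusion 6, Protocol 8.3 and the entry-criteria condition in 12.3.2 point the same way. The 12.3.1 entry has a harmless purpose in failure history and past-use stratification. Coding an enrolled verapamil user as Current Use would be factually correct, and no bias is shown.

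Much of this stands. The text leans toward ineligibility while on the drug, and the matter is a missing cross-reference of narrow reach. It does not close the third case above. Nothing says that the allowance is subject to the CYP3A4 bullet or that the 12.3.1 entry is limited to history, and exclusion 6 turns on whether the drug can be stopped or switched.

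A reader might infer a wider contradiction, because Protocol 4.4.1 allows "any antiemetic agent" and any opioid while aprepitant and buprenorphine are prohibited. The documents do not support that:

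- **Aprepitant.** Section 4.4.1 opens by allowing only what 4.4.2 does not specifically prohibit, and 4.4.2 names aprepitant. There is no conflict.
- **Buprenorphine.** It is named only in Attachment 12.2. But 4.4.2 bars the inhibitor class, says its examples are not exhaustive, and refers to that attachment. At most this is loose wording.

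Nor does it follow that participants in general are both eligible and ineligible. The 4.4.1 list concerns acute treatment during the study and is not an eligibility rule. For verapamil, two of the three cases have a clear answer.

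**Conclusion.** The concern holds in a narrow form. For a current verapamil user in Japan who could stop or switch but is willing to continue, the protocol both prohibits the drug and allows randomization on condition of continuing it, and no passage says which rule governs. The number affected is not given and may be zero; the figure of about 112 is not an estimate of it. No effect on sample size, power or type I error is shown.

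The conclusion assumes that no site instruction or deviation specification outside the two documents already settles the matter. It is worth acting on because it bears on participant safety, on consistent eligibility decisions and on the Current Use stratum, and the repair is small.

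**What to change.** Reconcile Protocol 4.3 (exclusions 5 and 6), Protocol 4.4.2 and Attachments 12.2, 12.3.1 and 12.3.2 so that one rule governs current verapamil users in Japan. State whether the verapamil entry in 12.3.1 serves past use and failure history only, or also concurrent use. The one-preventive allowance is repeated in Protocol 7.4.1 and SAP 10.3.1, which should follow the same rule. Which rule is clinically right is for the sponsor to decide.

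Then count the randomized participants in Japan with verapamil ongoing at screening or later, and code them all the same way, as deviations or not. This remains useful if enrolment has ended.

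The cost is a clarification letter or a footnote in the attachments, plus one line in the deviation specification. No change to the design or the analysis model is needed.

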4.4.3 Definition of Women of (Non-)Childbearing Potential and/or Acceptable Contraceptive Methods

For purposes of this study, women will be considered of childbearing potential unless they are naturally postmenopausal (ie, no menses for 2 years) or permanently sterilized (ie, bilateral tubal ligation, bilateral tubal occlusion [eg, Essure[®] placement⁴ with HSG confirmation], bilateral salpingectomy, bilateral oophorectomy, or hysterectomy). For women of childbearing potential who may participate in the study, the following methods of contraception, if properly used, are generally considered highly effective:

- Combined (estrogen and progestogen containing) hormonal contraception such as oral, intravaginal⁴, or transdermal⁴ (ie, pill, patch⁴, vaginal ring⁴)
- Progestogen-only hormonal contraception (with inhibition of ovulation) that are oral, injectable⁴, or implantable⁴

⁴ Contraceptive methods not approved in Japan

- IUD or IUS
- Vasectomized partner (provided that the partner is the sole sexual partner of study participant and that the vasectomized partner has received medical assessment of the surgical success)
- Sexual abstinence, defined as refraining from heterosexual intercourse for the entire duration of the study, from Visit 1 through the end of study (Visit 8/Follow-up Visit)
 - Note: Periodic abstinence (calendar, symptothermal, post-ovulation methods) is not an acceptable method of contraception. The reliability of sexual abstinence should be evaluated in relation to the duration of the clinical trial and the preferred and usual lifestyle of the subject.

Acceptable birth control methods which may not be considered as highly effective:

- Progestogen-only oral hormonal contraception (where inhibition of ovulation is not the primary mode of action)
- Male or women condom with or without spermicide⁴ (women and male condoms should not be used together)
- Cap⁴, diaphragm⁴, or sponge⁴ with spermicide
- A combination of male condom with either cap⁴, diaphragm⁴, or sponge⁴ with spermicide (double barrier methods) are also considered acceptable, but not highly effective, birth control methods

For males who may participate in the study, the following methods of contraception, if properly used, are generally considered reliable: post-bilateral vasectomy, barrier contraception, or sexual abstinence. Male participants must also refrain from donating sperm during the course of the study.

The investigator and each participant will determine the appropriate method of contraception for the participant during the participation in the study.

If a woman becomes pregnant during the study, the investigator will notify the sponsor immediately after the pregnancy is confirmed and the participant will be exited from the study after appropriate follow-up. The investigator will (1) notify the participant's physician that the participant was being treated with an investigational drug atogepant, and (2) follow the progress of the pregnancy. The investigator must document the outcome of the pregnancy and provide a copy of the documentation to the sponsor.

4.4.4 Special Diet or Activities

Participants should refrain from consuming grapefruit or grapefruit juice from the time the consent form is signed until completion of the study. Participants should also refrain from making significant changes to their diet or caffeine intake during the study.

Alcohol intake should be limited to no more than 1 drink per day throughout the study. A drink is defined as a 12-ounce (or 355 mL) can/bottle of beer, a 4-ounce (or 118 mL) glass of wine, or 1 ounce (or 30 mL) of liquor.

4.5 Screen Failures

Screen failures are defined as participants who consent to participate in the study but are not subsequently randomized to treatment. Rescreening of screen failures is permitted in certain situations (ie, failure to adequately screen due to COVID-19), with permission from the sponsor. However, participants with clinically significant laboratory values at Visit 1 (ie, screening; including ALT or AST $>1 \times$ the ULN, total bilirubin $> 1 \times$ ULN or serum albumin < 2.8 g/dL), or those with a positive UDS result at Visit 1 for recreational (including marijuana regardless of legality) or illicit drugs or non-disclosed⁵ concomitant medications are not allowed to be rescreened.

5. Study Interventions

5.1 Study Interventions and Formulations

Tablets containing atogepant 30 mg (Formulation Number 11280X) or atogepant 60 mg (Formulation Number 11281X).

5.2 Control Interventions and Formulations

Tablets containing matching placebo 30 mg (Formulation 011326X) for atogepant 30 mg and matching placebo 60 mg for atogepant 60 mg (Formulation 011317X).

⁵ For participants in the People's Republic of China, a positive UDS will result in screen failure regardless of disclosed concomitant medications.

5.3 Methods for Masking/Blinding

A double-dummy design will be used to maintain the blind. All study interventions will be provided in identical blister cards to maintain masking of the study.

All participants will be instructed to take their study intervention twice daily (ie, 2 tablets in the morning and 2 tablets in the evening) at approximately the same times each day. Participants, therefore, will receive either placebo BID, atogepant 30 mg BID, or a morning dose of atogepant 60 mg with an evening dose of placebo.

5.4 Treatment Allocation Ratio and Stratification

Approximately 750 participants will be randomized to one of three treatment arms in a 1:1:1 ratio as follows:

- Placebo (n = 250)
- Atogepant 30 mg BID (n = 250)
- Atogepant 60 mg once daily (n = 250)

Participant will be stratified by:

- Randomization will be stratified by use of acute headache medications during the baseline period (acute headache medication overuse Yes or No). Acute headache medication overuse (Yes) will be defined as follows: use of triptans on ≥ 10 days OR use of ergots on ≥ 10 days OR use of simple analgesics (ie, aspirin, NSAIDs, or acetaminophen) on ≥ 15 days OR use of any combination of triptans, ergots, or simple analgesics on ≥ 10 days.
- Approximately 70% of randomized participants will have taken at least 1 prior migraine prevention medication with proven efficacy (see [Attachment 12.3](#))⁶. Randomization will be stratified based on migraine prevention medication exposure (Current Use, Past Use, or Never Used) with proven efficacy. Participants with current or past use will be further stratified based on the number of medications failed with unique mechanisms of action: “failed 0 medications or failed 1 or more medication(s) with the same mechanism of action” or “failed 2 to 4 medications with different mechanisms of action” (see [Attachment 12.3](#)). Enrollment of participants with current use of a migraine prevention medication will be capped at ~15%.

⁶ All French participants must have taken at least 1 prior migraine prevention medication with proven efficacy to be eligible for Study 3101-303-002.

- Below are examples to illustrate how to implement the stratification based on prior migraine prevention medications:
 - Example 1: Participant has taken metoprolol and propranolol. According to [Attachment 12.3](#), these medications both belong to the beta-blocker pharmacologic category. This participant should be randomized to the “failed 0 medications or failed 1 or more medication(s) with the same mechanism of action” stratum.
 - Example 2: Participant has taken metoprolol, propranolol, and topiramate. According to [Attachment 12.3](#), metoprolol and propranolol belong to the beta-blocker pharmacologic category and topiramate belongs to the antiepileptic pharmacologic category. This participant should be randomized to the “failed 2 to 4 medications with different mechanisms of action” stratum.
 - Example 3: Participant has taken metoprolol and topiramate. According to [Attachment 12.3](#), metoprolol belongs to the beta-blocker pharmacologic category and topiramate belongs to the antiepileptic category; however, the patient stopped both of these medications because of a change in health insurance coverage and therefore did not meet the failure definition for either medication. This participant should be randomized to the "failed 0 medications or failed 1 or more medication(s) with the same mechanism of action" stratum.
- Randomization will be stratified by regions (ie, North America, Europe, Japan, China, Other)

